16.0 Request for Partial Waiver, Full Waiver, or Alteration of HIPAA Authorization

16.1 Describe how the use of PHI in this study poses no greater than minimal risk to participants' privacy.

There is no recruitment for this data but currently exists in our OWL database.

PHI including name, EMPI # and DOB are part of the patient database in OWL - we request to download data from OWL between 11.1.21-4.5.22

16.2 Describe why the research could not practically be carried out without the use of PHI.

This is retrospective data in our OWL database and does not involve recruitment.

16.3 Describe why the research could not be practically carried out without the waiver or alteration.

The psychiatry ambulatory clinic sees approx 250-300 patients per week - the PROMs are completed as part of clinical care. This is retrospective data in our OWL database and does not involve recruitment.

16.4 Do you assure that any data identifying subjects used in this study will not be disclosed to anyone other than the research team, sponsor, and oversight groups?

Yes No

16.5 Do you assure that you will not reuse or disclose this data for any other research unless you first receive IRB approval?

Yes No

16.6 Describe how you will utilize PHI for purposes of recruitment and describe how the use of PHI in this study poses no greater than minimal risk to participants' privacy.

There is no recruitment for this data but currently exists in our OWL database.

PHI including name, EMPI # and DOB are part of the patient database in OWL - we request to download data from OWL between 11.1.21-4.5.22

16.7 Describe why the research could not practically be carried out without the use of PHI for recruitment.

This is retrospective data in our OWL database and does not involve recruitment.

16.8 Describe why the research could not be practically carried out without the partial waiver for recruitment.

The psychiatry ambulatory clinic sees approx 250-300 patients per week - the PROMs are completed as part of clinical care. This is retrospective data in our OWL database and does not involve recruitment.

16.9 Do you assure that any data identifying subjects used in this study will not be disclosed to anyone other than the research team, sponsor, and oversight groups?

Yes No

16.10 Do you assure that you will not reuse or disclose this data for any other research unless you receive IRB approval?

Yes No

17.0

Research Settings/Performance Sites

17.1 Indicate the sites where research activities will occur, or from which subject data or specimens will be obtained, and a brief summary of the activities that will occur at each.

N/A (Select this option if this research is a Medical/Chart Review ONLY)

	Site	Summary
	CRMH	
	CRCH	
	CNRVMC	

		
	CFMH	
	JCHS	
	CRMH Rehab	Patients seen in, or referred to, ambulatory psychiatry clinic
	Riverside	
	Crystal Spring Medical Office Building	
	Other Carilion Clinic Physician's Office	
	Blue Ridge Cancer Care (BRCC) / US Oncology	
	Fralin Biomedical Research Institute at VTC	
	VT Blacksburg Campus	VT colleagues are involved in data management and analysis but no patients or patient care occurs at this location
	Assisted Living Facility or Nursing home	
	Other Locations (specify): 	

18.0

Applicable Regulations for ClinicalTrials.gov Registration

18.1 Is this study FDA-regulated?

Yes No

18.2 Is this research funded wholly or in part by NIH?

Yes No

18.3 Is this study a Clinical Trial, as defined by FDA or NIH, and therefore needing registration on ClinicalTrials.gov? Click the help button to the right to learn more about the definition of a clinical trial.

Yes No

18.5 Is the clinical trial already registered in ClinicalTrials.gov?

Not yet, but clinical trial will be registered prior to enrolling any subjects
 Yes
 No, this clinical trial will not be registered

ClinicalTrials.gov #:

Note: The following statement must be included verbatim in the consent form for trials that are/will be registered on ClinicalTrials.gov:

"A description of this clinical trial will be available on <http://www.ClinicalTrials.gov>, as required by U.S. Law. This website will not include information that can identify you. At most, the website will include a summary of the results. You can search this website at any time."

18.6 Who is responsible for registering this trial in ClinicalTrials.gov and ensuring information is updated, as necessary? Please provide a name if the person is at Carilion or listed on the research team, or state the sponsor or lead site if the sponsor or lead site will register the trial.

The responsible party for an applicable clinical trial (ACT) must register the trial and submit results information. The responsible party is defined as:

- **The sponsor of the clinical trial, as defined in 21 CFR 50.3; or**
- **The principal investigator (PI) of such clinical trial if so designated by a sponsor, grantee, contractor, or awardee, so long as the PI is responsible for conducting the trial, has access to and control over the data from the clinical trial, has the right to publish the results of the trial, and has the ability to meet all of the requirements for the submission of clinical trial information**

The responsible party for an ACT must submit the required clinical trial information **no later than 21 days** after enrollment of the **first** participant, but registration is highly recommended before enrollment begins due to some journal requirements.

[name] MD, CPI

19.0

Study Procedures

19.1 Provide a step-by-step description of the research procedures and/or and interactions with human subjects.

Provide a study schedule and list all activities or procedures that will be performed and describe the frequency and duration of research procedures, diagnostic and research tests, questionnaires or surveys, specimen collection, and experiments, including screening, intervention, follow-up etc in step-by-step chronological order. State the length of time subjects will be in the study and the expected amount of time required for each study visit or activity. Describe how, when and where research activities will be administered and analyzed. If the research includes blinding, indicate whether researchers or subjects will be "unblinded" to study assignment and describe when and how this will be done.

See Triage Program Working Details attached to this application for detailed description. Each survey is also included as attachments to this application.

Steps include:

The study will be introduced after the patient has completed the intake. At the end of the intake /assessment, the intake coordinator (team member) will describe the study to the potential participant and participant is able to confirm understanding about the study using the questions detailed in section 12.7. Consent is obtained either remotely or in-person, and a copy will be given to the patient in-person or emailed/mailed if remote. Introduction of the study will be, "We are researching if these measurements are helpful to people waiting for a psychiatric evaluation. Participation in the research is voluntary and you will be assigned randomly to either wait until your first appointment with your provider to complete these measurements again or complete these measurements every month until your first appointment with your provider." (The three measures they complete each month are the PHQ-9 depression, GAD-7 anxiety, and BASE-6 daily functioning). "Participation in this study is not linked to your psychiatric care – that is, it won't affect the wait-time to getting your initial appointment with your provider either way. Are you interested in participating in this study?"

1. If patient says yes, proceed to REDCap and complete consent process – you will need to set up a new participant record in RedCap and enter demographic information.
 1. Depending on which group the patient is assigned you will need to change the OWL Insights to not automatically send the inventories monthly if they are only in the 1x at onset group (no intervention).
2. Randomly assign patient into group (REDCap will do this when you start a new patient record); inform patient of the group they have been randomly assigned into to provide further instructions.
3. Provide all patients with CONNECT phone number at termination of the call.

Initial consenting process occurs after routine clinical psychiatry intake assessment by intake coordinator (if intake coordinator assesses that patient has capacity to pursue study discussion): 30-45 min consent process through REDCap or hard copy in-person. REDCap will be utilized to perform randomization. There is no blinding due to the nature of the wait-list control groups; both patients and investigators will be aware of study group assignment.

No intervention group randomization: no additional time/study procedures occur after consent; **SO C monthly PROMs DO NOT begin until after initial psychiatric provider evaluation for 6 additional months.**

Minimal intervention randomization: each month PROMs including PHQ-9, GAD-7 and BASE-6 are sent automatically for subject to complete via email or cell phone before initial psychiatric provider appointment - takes approximately 15 minutes to complete; watching microlearning videos about illness/symptoms takes approximately 15-30 minutes to watch depending on # videos recommended. Current wait-time for patients to see MD provider is 3-4 months; therefore, subjects in the minimal intervention group will participate in the study for up to 6 months before beginning regular treatment with provider.

PROM data from both groups will continue at initial psychiatric provider evaluation and monthly as is current clinical practice. Therefore, an additional 6 months of PROM data for each group will be followed to assess the research question of whether a no intervention or minimal intervention group may provide benefits to patients waiting to be seen and followed by psychiatric providers.

Total study participation time = 6-12 months depending on length of wait time before first psychiatric provider appointment

You must attach surveys, instruments, interview questions, focus group questions, etc. in the Initial Submission Packet and label them clearly.

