"Carilion Clinic cannot control the security of email or text messages once we send them, therefore we need your permission to text or email you the link to the e-Consent form for the study we discussed. Please be aware that while the email title will not include your disease status or symptoms, the body of the email will contain the link to the study. Someone else accessing your email/text messages could click on the link and read the consent, and therefore learn about your disease status or symptoms, which you may consider to be of a private or sensitive nature. Do you still wish to receive the link to the e-Consent via email/text?"

The permission to send the consent form via text or email will be documented in the individual's research record.

Once the investigator is on the phone or Amwell call with the potential participant, the investigator will ask the individual to verify their identity by using a combination of questions, including name, date of birth, and their specialist provider name. A passcode will be created from the first 3 letters of the subject's last name and their provider's last name. The link to the eConsent form will sent to the participant and will be accessed on the potential subject's personal

electronic devices (e.g., computers, portable tablets, smart telephones). The investigator will enter the passcode in REDCap and the potential participant will enter the passcode in order to access the consent. The investigator and potential participant will discuss the study and review the consent form page by page. If there is another study team member available, or the participant has a family member nearby, they will be asked to observe as a witness. The investigator will encourage the participants to follow along in the document and ask questions. The investigator will give the potential participant as much time as they would like either on the phone or after the call before the signing the consent. The participant will be told they can call the investigator with any follow-up questions. The investigator will document on the form by signing their name that they reviewed the consent with the participant and will document the date of this discussion.

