- the questions that the potential subject asked;
- whether a witness was required and present, and who the witness is;
- the time the potential subject was given to make their decision;
- how long the conversation lasted;
- how the participant received a copy of their signed document.

We are now requesting access to the baseline retrospective data that exists prior to the study. No recruitment or consenting were completed during this SOC.

13.6 How will you ensure that subjects or LARs have sufficient opportunity to consider whether or not to participate?

Check all that apply:

Subjects will be provided the consent form to take home for consideration prior to signing.
 Subjects will be allowed a waiting period to consider their decision.
 Other

Please specify waiting period:

48 hours-one week

13.7 How will the subjects' or LARs understanding of the consent information presented be assessed?

Check all that apply:

- Subjects will be asked to "Teach-Back" the study to the researchers
- Subjects will be asked open-ended questions about the research (purpose, procedures, risks, alternatives, voluntary nature)
- A tool or post-consent assessment will be used
- Other

Specify the "teach back" questions or open-ended questions that the subject will be asked to describe in their own words in order to assess their understanding.

Check for Understanding

1.I want to make sure that we have the same understanding about this research. Could you please tell me what this project is about in your own words?

2.Would you please walk me through what will happen if you agree to be in this study?

Randomized (like a flip of a coin) to either complete psychiatric intake assessment with an intake coordinator, including completion of PROMs OR complete psychiatric intake assessment with an intake coordinator, including completion of PROMs initially and monthly until provider appointment, AND be encouraged to watch videos about symptoms the patient is experiencing to learn about emotional illness and treatment approaches

3.What do you understand as the benefits and risks of this study, if you join?

Benefits: assessment of your symptoms to better pair you with a provider and assure timely provider assessment and treatment initiation; you may help determine ways to triage referrals to psychiatry that will be more helpful to patients in the future

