Risks: Completing measures of your symptoms may make you feel poorer emotionally as you complete them but the intake coordinator will be available to answer any questions or concerns and ensure you get timely provider assessment and treatment initiation

4.What will happen to you and your information if you decline to be a part of this study at any point?

You may withdraw at any point and your information will be destroyed. Your care at Carilion will not be affected.

5.Who will be able to see the information that you share with us?

Research Study Team and Carilion Clinic Institutional Review Board (IRB)

6.If you have any questions or concerns about the study, who will you contact?

[name]

Answers to these questions are required to ascertain understanding prior to signing consent document.

13.8 Utilizing eConsent has additional requirements. Please describe the following:

- The method to verify the identity of the individual providing consent;
- How participants will sign the eConsent (ex: type their name, use stylus or finger to sign);
- If potential participants will sign the consent while having a virtual conversation or if they will have additional time to consider their participation;
- If use of LAR is being requested, how you will ensure this individual is an appropriate LAR per Virginia requirements and verify their identity.

Verifying identification through two identifiers (name, DOB, address, contact info) over the phone, on Amwell or in-person

Sign econsent by typing their name

Sign the consent after virtual or in-person consultation either at the end of the initial discussion or up to one week for consideration of study involvement

LAR or witness NA for this study

13.9 If the enrollment of subjects who cannot read the consent form, due to visual impairment, literacy, or other issues, is anticipated, how will consent be obtained and documented?

Refer to 45 CFR 46.117(b)(2) or 21 CFR 50.27(b)(2) for information regarding when the use of a short form is appropriate. A witness to the consent process is needed.

- N/A
- Short form
- Other mechanism
- Consent form read to participant with witness present

13.10 How will you ensure research participants remain informed about the study and continue to agree to participate in the research study after their initial informed consent has been obtained?

- N/A

14.0 Request for Waiver, Alteration, or Waiver of Documentation of Consent for Adult Participants

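### Section 19.1 ties randomisation to opening the REDCap record, which is part of the consent step, so on the e-consent route concealment of the arm until signature is not assured

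*Combined protocol and SAP*

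**What the plan says.** The relevant text is in Section 19.1 (study procedures) and Sections 13.5 to 13.8 (consent).

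- **Step 1 of 19.1**, after a verbal yes: staff are to "proceed to REDCap and complete consent process – you will need to set up a new participant record in RedCap and enter demographic information".
- **Sub-step of step 1:** "Depending on which group the patient is assigned you will need to change the OWL Insights to not automatically send the inventories monthly". This action depends on the arm.
- **Step 2 of 19.1:** "Randomly assign patient into group (REDCap will do this when you start a new patient record". The patient is then told the group.
- **Section 13.5 (e-consent):** "The investigator will enter the passcode in REDCap and the potential participant will enter the passcode in order to access the consent". The same section states a preference for a video assessment with remote e-consent.
- **Section 13.8 (timing of signature):** "Sign the consent after virtual or in-person consultation either at the end of the initial discussion or up to one week for consideration". Section 13.6 gives the waiting period as "48 hours-one week".
- **Blinding (19.1):** there is none. Patients and investigators both know the group.

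Other text implies consent first. Section 11.5 makes agreement to be randomised an inclusion criterion, and the numbered list in 19.1 places consent in step 1 and assignment in step 2.

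**The concern.** The only event that the documents name as setting off allocation is the start of a REDCap record, and starting the record belongs to the consent step. If REDCap works as the sentence describes, an arm exists once the record is opened, whether or not the person has signed.

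The intake coordinator judges capacity, introduces the study and takes consent. In an open-label trial with self-reported outcomes, keeping the next assignment unknown until the person is committed is the main protection against selective enrolment. If the arm is visible beforehand, two things can go wrong:

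- Encouragement to sign, or the decision to sign, can depend on the arm.
- People who have been allocated but never sign can leave the arm without trace. Section 11.2 counts enrolment from consent, and the arm is not among the items that Section 22.6 lists for non-participants.

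Either would weaken the comparison of no intervention with minimal intervention, the only randomised comparison in the study.

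**Working it through.** The point concerns the order of events. The plan gives no figure to reproduce, so the passages are set side by side.

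1. **Trigger.** Section 19.1, step 2: start of a new REDCap record. Section 10.5 places randomisation after the coordinator judges the person eligible and capable of consent. It does not name a signed form as the condition.
2. **When the record is opened.** Section 19.1, step 1: within the consent step, after the verbal yes.
3. **REDCap before signature.** Section 13.5: staff enter a passcode in REDCap so that the person can open the form. On this route REDCap is in use before signature.
4. **Time from opening to signing.** Section 13.8 allows anything from the same discussion to one week. Section 13.6 gives 48 hours to one week.
5. **Who can see the arm.** Section 19.1: investigators are not blinded, and the coordinator operates the record.
6. **Safeguard.** No section says that allocation waits for a stored signature, and no concealment procedure is described.

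The order that follows on the e-consent route is: verbal yes, record opened (allocation, by the stated trigger), form reviewed, signature. Exposure differs by route:

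| Route | Can the arm exist before signature? | Length of exposure |
|---|---|---|
| E-consent, signed in the same discussion | Yes, if the record is opened first | Within the consent session, which 19.1 puts at 30–45 minutes |
| E-consent, signed later | Yes, if the record is opened first | Up to one week |
| Paper, signed before a record is opened | No | None |

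The steps also fit poorly with delayed signing. Step 2 assigns and informs the patient, and step 3 is tied to the end of the call. For someone who takes the permitted week, either steps 2 and 3 wait for a second contact that the text does not mention, or they come before the signature.

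The Owl sub-step adds little. It sits under step 1 although it needs the result of step 2, which shows that the list is not strictly in sequence. It does not show that allocation was meant to come first.

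**The case against.** The best case on the other side is that consent first was plainly intended. Agreement to randomisation is an inclusion criterion (11.5). Section 19.1 was to be completed in chronological order, and its list has consent before assignment. The introductory script speaks of assignment as still to come. The understanding check in Section 13.7 has the person describe both possible groups, and the answers are required before signing, which makes most sense if the arm is still unknown. Step 1 can also be read as consent first and record set-up afterwards. The trigger is a remark in parentheses, not a software specification. The REDCap build and the Triage Program Working Details, to which 19.1 refers for detail, are not available here, and either may hold a lock.

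Most of this stands as evidence of intent. It does not remove the stated trigger, and none of these passages says that allocation is held until signature. What remains is a conflict within the plan on a point that staff act on directly.

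A reader might infer two stronger things:

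- **That concealment is lost.** The documents do not show this. Exposure requires that the record is opened before signature and that REDCap really allocates at that moment. Paper consent signed first escapes it, and same-session signing leaves only a short interval.
- **That the error rate can be stated.** Suppose that 5–20% of one arm do not sign and that their PHQ-9 differs by 3–5 points. The arm mean would shift by 0.05 × 3 = 0.15 to 0.20 × 5 = 1.0 points. With 100 per arm and an SD of change of 6, the standard error is 6 × √(2/100) = 0.849, and the two-sided error would be about 9% at a shift of 0.5 and 22% at 1.0. The non-signing rate, the score gap and the SD are not in the documents. The calculation also carries a gap in score level in full into a test of change (Section 10.7), where much of a baseline difference cancels, and it assumes non-signing in one arm only. These error rates should not be used.

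**Conclusion.** The concern holds in a limited form. Followed as written on the preferred e-consent route, Section 19.1 allows the arm to be assigned and seen by the unblinded coordinator before signature, so allocation concealment is not assured. This contradicts the consent-first order implied by Section 11.5 and the step numbering, and the passages must be reconciled.

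The conclusion rests on two readings: that the record is opened before signature, and that REDCap allocates when it is opened. Both follow the wording, but neither can be confirmed without the REDCap build. The exposure is bounded at about one week per participant. How many participants were exposed, and any effect on the results, cannot be derived from the documents. Confidence is moderate. The change is worth making because it is cheap and protects the study's only randomised comparison.

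**What to change.** **Wording in 19.1.** Replace the remark that REDCap assigns the group at the start of a new record with: *randomisation is run in REDCap only after the signed consent is stored; the randomisation field is locked until then.* Move the Owl change after randomisation. If the build or the triage attachment already contains such a lock, one sentence in 19.1 saying so is enough.

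**Participants already enrolled.** Section 13.3 dates signed consents from 4.6.22 and the form is dated 03/16/2023, so new wording alone cannot protect those already in the study. Therefore:

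- Compare the allocation time with the signature time for every record.
- Report how many people had a record opened, consented and were randomised, by arm where one was assigned.
- List any case in which the arm was assigned before signature.
- Analyse all signed participants in their assigned arm. This does not recover people who were allocated and never signed, so their number by arm should be reported.

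**Cost.** One REDCap setting, a short edit to 19.1 and one check of timestamps. In conduct, people who do not sign during the first discussion need a second short contact to be randomised and told their group.
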